[figure not shown]
Pre-registration for quantitative part of Art on Prescription

[figure not shown]

Athens March, 10, 2024

Design

Stratified randomised controlled trial with two arms: arts intervention (any of the arts interventions, see list), which the investigators call here Active Group (AG) vs waitlist control (WL). Stratifying will happen at each site.

REMEMBER the investigators want to measure AG and WL, then WL becomes AG after 3 months and both the initial AG and the WL \rightarrow AG will be measured in exactly the same way for another 3 months.

AG for 3 months. Then goes into 3 month follow up.

WL for 3 months. Then this group receives intervention and becomes AG and has measurements for 3 months as the AG did.

There will be a 2-month break between T3 and T4 due to summer vacation

In the beginning, an open invitation to institutions of culture and mental health had been sent. Culture institutions i.e. Opera House, Contemporary Art Museum, National Theater etc. presented their action plans for interventional courses. Investigators did the connection between mental health and culture institutions.

Potential participants declared their preference for the interventional course such as dance, cinema etc. and they listed while an external investigator did the blind randomization into AG or WL group.

Measurement

Participants in both the AG and the WL groups will be measured on the following outcomes. Primary Outcome: Wellbeing Questionnaire (WEMWBS), PHQ-9, GAD-7 Secondary Outcomes: UCLA-20.

Frequency of Measurement:

→ The primary outcome will be measured at time points (for adults):

- T0: (before the randomisation; patient's personal data and demographics)
- T1: (before the start of the intervention for the active group or the entry into the study for the WL group)
- T2: 6 weeks (after the start of the intervention for the active group or the entry into the study for the WL group)
- T3: 12 weeks (after the start of the intervention for the active group or the entry into the study for the WL group)

The secondary outcomes will be measured at time points 0 (T4) and 12 weeks (T5) for both AG and WL.

→The primary outcome will be measured at time points (for children/adolescents):

- T0: (before the randomisation; patient's personal data and demographics)
- T1: (before the start of the intervention for the active group or the entry into the study for the WL group)

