- T3: 12 weeks (after the start of the intervention for the active group or the entry into the study for the WL group)

The secondary outcomes will be measured at time points 0 (T4) and 12 weeks (T5) for both AG and WL.

Model

The investigators will follow standard practice for RCTs and apply an ANCOVA model to estimate the effects of treatment. The formalism is:

y ~ b0 + b1xtreatment_group + b2xtime + b3xtreatment_groupxtime + covariates (1)

Where, y is each outcome, b1-b3 are the regression coefficients and covariates denote covariates at randomisation (DETERMINE)

The inference of interest for the model concerns b3, the interaction term, as the investigators posit that there will be a difference in slopes between the treatment groups.

The inference is going to happen via an estimation of the t-statistic, defined as follows"

t = b3/SE(2)

Where SE is the standard error for coefficient b3

[figure not shown]
t > 1.96(3)

And 1.96 is the critical value for statistical significance at alpha = 0.05.

Target Sample Size per Arm

Parameters:

- power = 0.8
- alpha = 0.05
- Correlation between time points = 0.6 (a conservative estimate based on https://www.ncbi.nlm.nih.gov/pmc/articles/PMC2222612/)
- Effect size corresponding to d = 0.5

library(tidyverse) # for data wrangling library(faux) # for simulation

library(broom) # for tidy analysis results

set.seed(1974)

I will simulate the following

```

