# two groups, treatment and WL control.
# they start off with distributions with the same mean and sd (due to randomisation)
# the WL control stays the same, the treatment group changes to arrive at a d = 0.4, which i
# what investigators stipulated in advance
# the shape of the change should not matter that much for this linear model calculation

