# here come the parameters that I will pass to this function
# from https://hqlo.biomedcentral.com/articles/10.1186/1477-7525-10-156
mean T1 <- 43.5 # the biggest trial in that list, the PEIP
sd T1 <- 10.4 # from that trial
d <- -0.5 # stipulated effect size of difference

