# to create equally spaced value, my idealised decline of values
the treatment means <- seg(mean T1, mean T4, length.out = 4)

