# Now I will loop this function over a number of different sample sizes
# this is the list of sample sizes
n per arm <- seq(20,300, by = 20)

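### Three unranked primary scales are each tested at an unadjusted 1.96 with no success rule: if any one may be claimed, correctly modelled tests give 8.4% to 14.3% two-sided false-positive risk, and the 0.8 power is per outcome, not joint

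*Protocol*

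**What the plan says.** Protocol, Measurement: "Primary Outcome: Wellbeing Questionnaire (WEMWBS), PHQ-9, GAD-7 Secondary Outcomes: UCLA-20". The three primary scales carry no ranking. The next lines turn to the singular: "The primary outcome will be measured at time points (for adults".

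Protocol, Model: one regression is specified for all outcomes ("Where, y is each outcome, b1-b3 are the regression coefficients"). The inference is on b3, the group-by-time interaction, through t = b3/SE. The decision threshold is printed: "And 1.96 is the critical value for statistical significance at alpha = 0.05". No sentence says whether one, a named one, or all three scales must pass it.

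Protocol, Target Sample Size per Arm: power 0.8, alpha 0.05, correlation between time points 0.6 and d = 0.5 are listed once. The code simulates a single score, and one of its comments gives a different effect ("the treatment group changes to arrive at a d = 0.4"). The code runs over a grid of sizes, "n per arm <- seq(20,300, by = 20"), and no final N is stated.

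**The concern.** The same printed threshold gives different trial-level error rates under different success rules, and the protocol states no rule. A flat 1.96 is right if all three scales must be significant, or if they are tested in a fixed order that stops at the first failure. It is too lenient if any one of three may be claimed. Power depends on the rule as well: a per-outcome target of 0.8 is neither the chance of winning on all three scales nor the chance of winning on at least one. With no rule fixed in advance, one significant scale out of three has no agreed confirmatory meaning.

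**Working it through.** **Inputs from the protocol.** Three primary outcomes; b3 tested for each; critical value 1.96; alpha 0.05; power 0.8; d = 0.5 (0.4 in a code comment); within-person correlation r = 0.6 in the parameter list and 0.5 in the code.

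**Assumed.** The correlation rho between the three test statistics, shown from 0 to 0.9. Normal statistics with the same rho for each pair.

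**The plan's own figure.** 2 × (1 − Φ(1.96)) = 0.0500, so the stated alpha reproduces as a two-sided level for one test. The upper tail alone, which is how the inequality is printed, would be 0.0250.

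**Any one of three, global null, two-sided.** With rho = 0: 1 − 0.95³ = 0.1426. For rho > 0, with c = 1.96:

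P(none) = ∫ φ(w) [Φ((c − √rho·w)/√(1 − rho)) − Φ((−c − √rho·w)/√(1 − rho))]³ dw

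| rho | 1.96 for each | Bonferroni, 2.394 for each |
|---|---|---|
| 0 | 14.3% | 4.9% |
| 0.3 | 13.6% | 4.8% |
| 0.5 | 12.5% | 4.5% |
| 0.7 | 10.9% | 3.9% |
| 0.9 | 8.4% | 3.0% |

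Under the global null, Holm makes at least one rejection exactly when Bonferroni does, so the last column also applies to Holm. If only a benefit counts, with all scales scored in the same direction, three tests at 1.96 give 7.3% (rho 0) to 4.2% (rho 0.9), against 2.5%.

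**Equation (1) fitted literally.** It has no participant term. The residual variance then includes the between-person part, and the b3 statistic has null standard deviation √(1 − r) instead of 1. The size per outcome is 2 × (1 − Φ(1.96/√(1 − r))):
- r = 0.5: 1.96/0.707 = 2.77, size 0.56%
- r = 0.6: 1.96/0.632 = 3.10, size 0.19%

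For any of three, the bound at r = 0.5 is 3 × 0.56% = 1.7%.

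**Power at the stated target.** 80% per scale at two-sided 0.05 means a mean statistic of 1.960 + 0.842 = 2.802.
- All three significant, equal effects: 0.8³ = 51% (rho 0), 61% (0.5), 66% (0.7), 72% (0.9).
- At least one significant at 1.96: 1 − 0.2³ = 99% (rho 0), down to 87% (0.9).
- Holm's strictest step (0.05/3 = 0.0167, critical 2.394): Φ(2.802 − 2.394) = Φ(0.408) = 66% per scale.

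**What size that is.** For a within-person slope test on T1 to T3 with the full d reached at T3, SE = σ√(4(1 − r)/n). Hence n = 4(1 − r) × 2.802²/d². With r = 0.5 and d = 0.5: 2 × 7.85/0.25 = 62.8, about 63 per arm.

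**If N is larger.** The protocol's own ANOVA without a participant term, at r = 0.5 and d = 0.5, reaches about 80% near 150 per arm. At that assumed N the correct slope test has SE = σ√(2/150) = 0.1155σ:
- d = 0.5: z = 4.33; power 99% at 0.05, 97% at 0.0167
- d = 0.4: z = 3.46; power 93% at 0.05, 86% at 0.0167

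These power figures assume equal d on all scales, no dropout and no clustering.

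**The case against.** The strongest defence has three parts.

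*Success rules and multiplicity are commonly left to the SAP, and none was available for this review.* That is fair for a protocol that is silent. This one prints a decision threshold for each outcome, so an SAP that adjusted for three primaries would have to override it. It is also true that 0.05 at 1.96 is a correct statement about one test, and that the protocol nowhere claims a 5% trial-wide error or a win on any one scale. What stands against the plan is an ambiguous rule with an unadjusted threshold, not a false statement about the trial-level error.

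*The model as written is conservative.* A reader might infer that the trial, run literally, carries an 8% to 14% false-positive risk. The document does not support that: equation (1) without a participant term stays at or below about 1.7% for any of three. But this is a by-product of a wrong standard error, which is a separate defect and no form of multiplicity control. It disappears once repeated measures are modelled properly, and the 8.4% to 14.3% then applies.

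*The power calculation is not tied to one scale.* A reader might infer from "mean T1 <- 43.5 # the biggest trial in that list, the PEIP" that the 0.8 covers WEMWBS alone, since 43.5 exceeds the maximum of PHQ-9 (27) and GAD-7 (21). That inference fails. The simulated power depends on the standardised effect, the correlation and n, not on the mean. With the same d and r, 0.8 holds separately for each scale. Only the narrower point stands: it is a per-outcome target, not joint power.

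**Conclusion.** The point holds in conditional form. Three unranked primaries are each tested at an unadjusted 1.96, and the rule that would give that threshold a trial-level meaning is missing.

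The 8.4% to 14.3% rests on three conditions: any one scale may be claimed, repeated measures are correctly modelled, and the correlation between test statistics lies between 0.9 and 0. Every value in that range exceeds 5%. Under an all-three rule or a fixed order, type I error is not inflated. An all-three rule then costs joint power: 51% to 72% where each scale has 80%.

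It would also be too strong to say that adjustment costs almost nothing. The small losses at 150 per arm rely on surplus power created by sizing with the faulty ANOVA. At the protocol's own 80% target the loss is material. As no final N is stated, the true cost cannot be pinned down further. This should be corrected, but it does not invalidate the design.

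**What to change.** Amend the protocol before outcome data are examined. Keep the inference on b3, state the success rule, and choose one of:

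1. **Three primaries with Holm** in place of the flat 1.96. At a size giving 80% per scale, the strictest step leaves about 66%.
2. **One named primary, the other two in a stated fixed order**, each at 0.05, stopping at the first non-significant result. The scale in first place loses no power, but a later scale cannot be claimed if an earlier one fails. The investigators must choose the order. The simulation does not settle it: 43.5 fits only the WEMWBS range (14 to 70), yet the simulated path ("to create equally spaced value, my idealised decline of values") would be a worsening on that scale.
3. **All three required**, each at 0.05. Joint power is 51% to 72% at a size giving 80% per scale.

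Then restate power for the chosen rule from a model that accounts for repeated measures within a participant, at the actual N. The work is one amendment and a rerun of the simulation; no increase in enrolment is asked for. The loss shrinks if N is larger: at an assumed 150 per arm with r = 0.5, Holm's strictest step takes power from 99% to 97% at d = 0.5, or from 93% to 86% at d = 0.4.

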# what should matter are
# a) sds which I will keep the same as in baseline
# b) number of measurements, stipulated to be n = 4

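### UCLA loneliness, the only secondary outcome, is measured only after the randomised period, so the planned group-by-time test on it does not compare arts with waitlist

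*Protocol*

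**What the plan says.** UCLA-20 is the only secondary outcome listed under Measurement. Under Frequency of Measurement the same sentence closes both the adult and the child/adolescent schedule: "The secondary outcomes will be measured at time points 0 (T4) and 12 weeks (T5) for both AG and WL". The T1–T3 entries in both schedules are for the primary outcome, and T0 covers personal and demographic data only.

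The Design section says what each arm is doing by then. For the active group: "AG for 3 months. Then goes into 3 month follow up". For the waitlist group: "WL for 3 months. Then this group receives intervention and becomes AG and has measurements for 3 months as the AG did". It also places T4 in the calendar: "There will be a 2-month break between T3 and T4 due to summer vacation".

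The Model section does not separate secondary from primary outcomes: "Where, y is each outcome, b1-b3 are the regression coefficients". It then fixes the test: "The inference of interest for the model concerns b3, the interaction term". The tool description says that higher UCLA scores are worse.

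**The concern.** The randomised comparison of arts with waitlist runs from T1 to T3. On the printed schedule no UCLA score is taken in that window, and AG has no UCLA score from before its course. The only two scores are taken when AG has finished its course and WL is due to receive it.

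A group-by-time test on those two scores compares AG's change in follow-up with WL's change under intervention. If the intervention reduces loneliness, WL should fall over T4–T5 while AG stays flat or drifts back. With arms coded as randomised, a real benefit would then appear as no effect or as an effect in the harmful direction.

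An analysis plan cannot repair this later, because scores not collected at T1 and T3 cannot be recovered.

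**Working it through.** **No figure to reproduce.** The protocol prints no sample size, power or expected effect for UCLA. The check is therefore of what b3 estimates on T4–T5, followed by an illustration of its size.

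**Inputs from the protocol.** d = 0.5, correlation between time points r = 0.6, and critical value 1.96. The simulation code sets r = 0.5, so that value was run too.

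**Assumptions.** These d and r values were set with WEMWBS in mind and are borrowed for UCLA. The arm sizes of 50 and 100 are illustrative, since the visible text gives no final target. SD is 1 and arms are coded as randomised (AG = 1). The protocol gives no carry-over figure, so a range is shown.

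**What b3 estimates.** Let d be the benefit of one course in SD units, and let f4 and f5 be the fractions of AG's benefit present at T4 and T5.

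- AG means at T4 and T5: −d·f4 and −d·f5.
- WL means at T4 and T5: 0 and −d.
- b3 on T4–T5 = (−d·f5 + d·f4) − (−d) = d(1 + f4 − f5).
- b3 on T1–T3, the intended comparison, = −d.

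For any f4 and f5 between 0 and 1, the T4–T5 value is zero or positive, so it never has the sign of benefit. A negative value requires AG to improve more in follow-up than WL does under intervention. This result needs no assumption about n or r.

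**How often the wrong direction is significant.** Simulation with 10,000 runs per cell, r = 0.6, WL going from 0 to −0.5, and AG at −0.5 at T4. Entries are the share of trials with t > 1.96 at 50 / 100 per arm.

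| AG over T4–T5 | AG at T5 | mean b3 | subject-level SE | OLS SE, no subject term |
|---|---|---|---|---|
| improves as much again | −1.00 | 0.00 | 2.5% / 2.8% | 0.1% / 0.1% |
| improves half as much | −0.75 | +0.25 | 28.4% / 50.5% | 4.5% / 12.6% |
| keeps its gain | −0.50 | +0.50 | 78.9% / 97.9% | 38.6% / 81.0% |
| loses half | −0.25 | +0.75 | 98.5% / 100% | 86.0% / 99.8% |
| loses all | 0.00 | +1.00 | 100% / 100% | 99.3% / 100% |

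The Model section does not say how the standard error is obtained. The OLS column follows the sample-size code, which fits the model without a subject term.

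**Closed-form check, AG keeps its gain, n = 50.**

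- Subject-level SE = √(2(1 − 0.6)) × √(2/50) = 0.894 × 0.2 = 0.179. Then 0.5/0.179 − 1.96 ≈ 0.84, which gives about 80%.
- OLS SE = √(4/50) = 0.283. Here t has mean 0.5/0.283 = 1.77 and SD 0.179/0.283 = 0.63, which gives about 38%.

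Both agree with the simulation. With r = 0.5 the shares at 50 / 100 per arm are 70.4% / 94.5% (subject-level) and 39.6% / 78.1% (OLS).

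The problem is symmetric. At 51 per arm a change-score test on T1–T3 has power 0.806 in the right direction. If AG keeps its gain, the T4–T5 test has the same 0.806 chance of significance in the wrong direction.

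**What the other contrasts offer** (two-sided 0.05, 50 / 100 per arm):

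- T1 and T3 with baseline-adjusted ANCOVA, standardised effect 0.5/√(1 − 0.36) = 0.625: 87% / 99%.
- T3 between arms only: 70% / 94%.
- T4 between arms, if taken before WL starts: 70% / 94% if all of the 0.5 SD persists, 46% / 75% if a quarter fades (0.375), and 24% / 42% if half fades (0.25).

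**The case against.** The strongest reply is that T4 and T5 are a labelling slip for T1 and T3. The time points 0 and 12 weeks fit the first phase, UCLA is listed beside the primary outcomes, and the Design section says of the second phase that the initial AG and the WL→"AG will be measured in exactly the same way for another 3 months". Read generously, that implies UCLA in the first phase too. A slip is possible. But the labels appear in both schedules, the Design section separately places T4 after the summer break, and no sentence assigns UCLA to T1 or T3. Staff following the schedule would miss the baseline either way.

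Second, the protocol does not say that the model will be fitted to T4–T5 with arms coded as randomised. This stands: the sign depends on the coding. Recoding WL as active restores the sign, but the comparator is then an arm that has already been treated. If both groups are called AG, group does not vary and b3 cannot be estimated. No coding gives arts versus waitlist.

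Third, the percentages are conditional. This stands too: they run from about 0.1% to 100% across the scenarios and are illustrations only.

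Fourth, a reader who knows that WL is under treatment might read its larger fall as a treatment response rather than as harm to AG. That is fair, but the named test would still not measure what the protocol says it measures.

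Finally, T4 is not worthless. If it is taken before WL starts, it is a randomised contrast of treated with untreated, only delayed. The protocol neither names that contrast nor states when WL starts relative to T4.

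**Conclusion.** The concern holds on the printed text. UCLA has no score in the T1–T3 randomised period, and the b3 test that the Model section applies to every outcome does not estimate arts versus waitlist on T4–T5. With arms coded as randomised, b3 is null or wrong-signed unless AG improves more than WL; that follows from the schedule and the crossover alone. The size depends on borrowed d and r, assumed arm sizes and AG's course in follow-up. If AG keeps its gain, b3 is +0.5 SD, with the wrong direction significant in 79% / 98% of trials (subject-level SE) or 39% / 81% (OLS SE) at 50 / 100 per arm.

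The one randomised UCLA contrast left, at T4, has no baseline adjustment and loses power if the effect fades over the break. The three primary outcomes keep their T1–T3 measurements, so the damage is confined to the secondary outcome. It should be fixed.

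A related inconsistency is that the Design section promises like-for-like measurement in the second phase, while the primary-outcome schedule stops at T3 and the simulation assumes four occasions ("number of measurements, stipulated to be n = 4"), labelled T1 to T4.

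**What to change.** - Schedule UCLA in both arms at T1 and T3, in the adult and the child/adolescent schedules, and base the randomised secondary analysis on those visits. If T4/T5 was a slip for T1/T3, correct the sentence in both places.
- State that the b3 test is not applied to T4–T5. Report T4–T5 change descriptively: maintenance in AG and within-arm change in WL.
- If T1 has passed (randomisation is described in the past tense), use the T3 between-arm comparison.
- If T3 has passed too, use the T4 between-arm difference, state that T4 is taken before WL starts, and report it as a delayed post-treatment contrast.
- Reconcile the Design statement on second-phase measurement with the primary-outcome schedule.
- State which UCLA form is used, since Measurement names the 20-item scale and the tool description also presents the 3-item version.

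The cost is one self-report form at two visits that already take place, plus edits to the schedule and the analysis text. No visit is added. The burden depends on the form chosen. The T3-only fallback has lower power than T1–T3 (70% / 94% against 87% / 99%), and T4 has less still if the effect fades.

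### The test of b3 is an unadjusted change-from-T1 comparison, not a baseline-adjusted ANCOVA, and gives up about 20–25% of variance over the randomised visits

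*Protocol*

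**What the plan says.** The Model section of the protocol announces the method: "The investigators will follow standard practice for RCTs and apply an ANCOVA model to estimate the effects of treatment". The equation given for it is "y ~ b0 + b1xtreatment_group + b2xtime + b3xtreatment_groupxtime + covariates (1"). The covariates are a placeholder: "covariates denote covariates at randomisation (DETERMINE"). The test is fixed: "The inference of interest for the model concerns b3, the interaction term". Its rationale is an expected divergence of the arms over time: "as the investigators posit that there will be a difference in slopes between the treatment groups".

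The Measurement section defines the first and last outcome visits of the randomised period as "T1: (before the start of the intervention for the active group or the entry into the study for the WL group") and "T3: 12 weeks (after the start of the intervention for the active group or the entry into the study for the WL group"). Adults also have T2 at 6 weeks; children and adolescents have T1 and T3 only.

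Equation (1) does not list the levels of time, but two places show that T1 is one of them. The simulation code makes T1 the first level of the response and has no baseline covariate. For children, a slope exists only if T1 is on the outcome side.

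The parameters under Target Sample Size per Arm include "Correlation between time points = 0.6 (a conservative estimate based on" a cited paper. The code below them sets the correlation to 0.5.

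**The concern.** In a randomised trial, ANCOVA usually means regressing the post-intervention score on arm with the baseline score as a covariate. Equation (1) does something else: it estimates a separate T1 level for each arm (b1) and then compares slopes. Yet the notes in the code accept that the arms start with equal means because of randomisation. Estimating a difference known to be zero in expectation spends information.

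Two things are at stake. The first is precision: the trial needs more participants for the same power, or has less power at the same size. The second is a trap in the placeholder. If T1 is written in as a covariate, the team may believe the test has become baseline-adjusted when b3 has not moved.

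**Working it through.** **Inputs.** Visits at 0, 6 and 12 weeks (Measurement); r = 0.6 (text) or 0.5 (code); d = 0.5 (text and code) or 0.4 (a code comment); power 0.8 and two-sided alpha 0.05; SD constant over time (code). As the protocol gives a single r, equal correlation between all visits is assumed. The protocol prints no sample size and no achieved power, so there is no figure of its own to reproduce.

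**1. What b3 estimates.** With three equally spaced visits and linear time, the slope weights on T1, T2, T3 are −1/2, 0, +1/2 per 6-week step. Over 12 weeks they are −1, 0, +1. So b3 over 12 weeks is the between-arm difference in mean T3 − T1. In one simulated data set (100 per arm, r = 0.6), ordinary least squares, a random-intercept model and the raw change-score comparison all gave −7.043.

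**2. Whether the open covariates repair it.** A covariate that is constant within a person and enters as a main effect is orthogonal to the within-person time contrast in complete balanced data. Adding T1 to the same data left b3 at −7.043. ANCOVA of T3 on T1 gave −6.982, with SE 1.112 against 1.296 for the change score. In a second simulated data set, adding T1 and site as main effects left b3 at 0.44576. Only a T1-by-time term, which equation (1) lacks, moved it to the ANCOVA value of 0.43341.

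**3. Variance over three visits.** In units of SD²/n, for the difference between two arms of n each:

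- b3 with a valid within-person SE: 2 × 2(1 − r)
- T3 ANCOVA on T1: 2 × (1 − r²)
- ratio: (1 − r²) / [2(1 − r)] = (1 + r)/2

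| r | b3 | ANCOVA | reduction |
|---|---|---|---|
| 0.6 | 1.60 | 1.28 | 20% |
| 0.5 | 2.00 | 1.50 | 25% |

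Simulation of 20,000 trials with three visits gave reductions of 19.8% and 24.4%.

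**4. Variance over the code's four visits.** With four equally spaced visits and linear time, the full-span weights are −0.9, −0.3, 0.3, 0.9, whose squares sum to 1.8. The variance of b3 is 2 × 1.8(1 − r) = 1.44 (r = 0.6) or 1.80 (r = 0.5). A last-visit ANCOVA has 1.28 or 1.50, so the gain is 1 − 1.28/1.44 = 11% or 1 − 1.50/1.80 = 17%.

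**5. Illustrative n per arm.** n = (1.960 + 0.842)² × V/d², where the squared term is about 7.85, rounded up:

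| d | r | b3 | ANCOVA |
|---|---|---|---|
| 0.5 | 0.6 | 50.2 → 51 | 40.2 → 41 |
| 0.5 | 0.5 | 62.8 → 63 | 47.1 → 48 |
| 0.4 | 0.6 | 78.5 → 79 | 62.8 → 63 |
| 0.4 | 0.5 | 98.1 → 99 | 73.6 → 74 |

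Where b3 has 80% power, the standardised effect is 2.802. Dividing by √0.80 or √0.75 and subtracting 1.960 gives 1.17 or 1.27, so ANCOVA has about 88% (r = 0.6) or 90% (r = 0.5).

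**6. Chance imbalance.** If the arms differ by δ at T1 by chance, the expected T3 difference carries over only rδ. The change contrast is therefore shifted by −(1 − r)δ: 0.4δ at r = 0.6 and 0.5δ at r = 0.5. ANCOVA removes this shift.

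**The case against.** The strongest reply is that comparing slopes is a legitimate analysis of a randomised trial and is the hypothesis the investigators state. This stands as far as validity goes. A reader might infer that b3 is biased or that its test is invalid for want of baseline adjustment; the documents do not support that. Under randomisation the T1 difference is zero on average, so imbalance adds variance and not bias. But over the randomised visits the expected slope difference and the expected T3 difference are the same quantity when the arms start equal, so the adjusted analysis answers the same question more precisely.

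The label is partly a matter of usage: a linear model with group, continuous time, their interaction and covariates can be called analysis of covariance in the general sense. That softens the complaint about the name but not the lost precision.

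The gain depends on layout and correlation. It is (1 − r)/2 over three visits, so 15% at r = 0.7, and it is smaller under the code's four visits. A reader might also take 51 to 41 as a saving on the planned trial. That does not follow: no N is printed, and rerunning the code's logic at d = 0.5 gives power of 0.78–0.79 at 140 per arm and 0.83–0.84 at 160. That code fits no participant term, which is a separate matter; the comparison here assumes it has been put right.

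Finally, it is tempting to fault b3 for ignoring T2. A T3 ANCOVA ignores it too. A common-T1-mean model with time as a factor has a T3 variance of 1.28 at r = 0.6 with or without T2 in complete data.

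**Conclusion.** The point holds as one of efficiency and should be changed, but it does not threaten validity. b3 is the unadjusted T3 − T1 contrast, and main-effect covariates cannot turn it into a baseline-adjusted one. Over the randomised visits the avoidable variance is 20% at r = 0.6 and 25% at r = 0.5; under the four-visit layout a last-visit ANCOVA saves about 11% and 17%. These figures rest on equal correlation between visits, constant SD, complete data, linear time in equation (1) and a valid within-person standard error.

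A reader might also infer that the gain is free of conditions, because T1 is collected anyway. The documents do not quite support that. T0 is placed before randomisation, whereas T1 is tied only to the start of treatment or study entry and could follow allocation. Treating the T1 means as equal requires that knowledge of allocation has not affected T1. The present contrast leans on T1 in the same way.

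**What to change.** Make the primary contrast the AG–WL difference at T3, adjusted for the T1 score and for site, which is the randomisation stratum. Alternatively, use a repeated-measures model with a participant-level covariance and a T1 mean common to both arms. In that model T2 helps mainly when data are missing, or if a linear effect is assumed: the variance at r = 0.6 is then 1.257 instead of 1.28.

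Replace the covariate placeholder with these named terms and use the same model in the power simulation. State that T1 is measured before participants learn their allocation, or confirm when it is taken.

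The cost is a reworded Model section and a changed model line in the simulation, which is then rerun. No visits, participants or data are added.
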